In September 2015, a new FDA-approved test became available at Beaumont, computed tomography-derived fractional flow reserve (CT-FFR, provided by HeartFlow, Inc.), that provides flow information directly from computational fluid dynamic analysis of CCTA images without further testing^{7- 15}. This analysis does not involve any additional imaging, contrast or medications. CT-FFR has been shown to be more accurate in predicting the presence of true ischemia on invasive fractional flow reserve testing in the invasive catheterization laboratory (CATH-FFR). Patients managed by CATH-FFR have been shown to have better outcomes than patients managed using visual inspection of CATH stenosis alone. The standard cutoff for an abnormal CATH-FFR and CT-FFR is the measurement of a blood pressure drop of $\geq 20\%$ (FFR ≤ 0.80) across a given stenosis.

For Beaumont ED patients, CT-FFR has been in use on a research basis since September, 2015, but is not considered standard of care. Since September 2015 we have conducted a study to analyze clinical outcomes after CT-FFR, (a sub-analysis of HIC #2016-157, the Beaumont CT Registry). We have collected, analyzed data and submitted for publication, data on 147 ED patients with CCTA stenosis of 25-99% managed with CT-FFR and followed for a minimum of 90 days. These data show no evidence to date of increased risk, but do show improved prediction of the need for revascularization using CT-FFR (see Appendix, submitted for publication).

The objective of the present trial is to evaluate the CATH rate and diagnostic effectiveness of CT-FFR as compared to a standard of care diagnostic strategy (SOC) in the management of ACP patients with intermediate-to-severe stenosis on CCTA.

Hypotheses:

Primary Hypothesis:

Cardiac Catheterization Rate: Use of CT-FFR will reduce the CATH rate in ACP patients with >50% stenosis on CCTA. There will be a pre-specified subset analysis of the Intermediate (51-70%) and Severe (71-90%) stenosis groups.

Secondary Hypotheses:

1. Diagnostic Effectiveness: CT-FFR results will more accurately triage patients to CATH compared to patients triaged by SOC. True flow-limiting coronary stenosis will be defined by CATH-FFR as the gold standard in patients undergoing CATH. Accurate triage will be calculated as the proportion of patients with correct triage to CATH based on CATH-FFR results:

CT-FFR group:

True positive case: CT-FFR positive and CATH-FFR positive

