True negative case: CT-FFR negative and CATH-FFR negative

Proportion of correct CT-FFR triage = (True positive + True negative) / All CATH

SOC group:

True positive case: SOC chosen by attending physician for CATH confirmed by CATH-FFR. By definition, the clinicians' decision to CATH based on clinical evidence is considered an SOC positive case, there can be no SOC true negative cases that go to CATH.

Proportion of correct SOC triage = True positive / All CATH

2. Safety: Patients following CT-FFR-guided management will have similar MACE rates, including death, ACS and unanticipated late revascularization when compared to SOC-guided patients.

Methods

Study Population

The study population will be drawn from ED ACP who have already undergone CCTA for diagnosis, and have been found to have 50% or greater stenosis but less than 90% of at least one coronary branch. Two-hundred patients meeting entry criteria will be enrolled from a sample of ED ACP patients at Beaumont Hospital (Royal Oak). These patients will be randomized 1:1 using sealed envelopes provided by the study statistician, to either standard of care (SOC) or CT-FFR management. (See Figure 1. Study Diagram)

Inclusion Criteria

1. Emergency department or inpatients admitted through the ED with chest pain suspicious for ACS based on history and physical examination.
2. At least one biomarker (troponin) and electrocardiogram with no evidence of definite ACS.
3. A completed CCTA demonstrating $\geq 50\%$ but $< 90\%$ stenosis of at least one coronary artery branch.
4. CCTA test images with sufficient diagnostic quality for CT-FFR analysis.
5. Ability and willingness to provide informed consent.

Exclusion Criteria

- 1 Left main coronary stenosis of 50% or greater.
- 2 CCTA lesions demonstrating stenosis >90% ("subtotal"), or complex, high-risk plaque characteristics resulting in an a priori recommendation for triage to CATH by CCTA interpreting physician.
- 3 Attending physician a priori decision for CATH.
- 4 Prior coronary stent, coronary bypass or prior known myocardial infarction.
- 5 Clinical instability, such as hypotension, signs of shock, and/or unrelieved or accelerating chest pain.
- 6 Pregnancy

Obtaining Consent

Consent will be obtained by a co-investigator. Patients will have at least 20 minutes to consider whether they wish to consent.

Screening Log

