A screening log will be maintained by research coordinators of all patients who were considered for enrollment and their demographics, clinical characteristics and the reason for their exclusion.

Sample Size

Our primary outcome is the CATH rate at 3 months. Based on our previous analyses from our IRB 2016-157 study (the FFR-ACP study), the SOC arm had a 89.5% CATH rate in the 71-99% stenosis group and 58.3% in the 51-70% stenosis group. With the 51-70% stenosis group having twice as many patients as the 71-99% group, we anticipate 68.7% of CATHs in all SOC controls. In our previous CT-FFR negative patients, there were 65.6% CATHs in the 71-99% stenosis group and 21.3% in the 51-70% stenosis group. Again with a 2 to 1 ratio, we anticipate an overall CATH rate of 36.1% in the FFR patients. Since these are estimates for the FFR group, we calculated several possibilities. All have 90% power with a significance level of 0.05%.

We determined a sample size of 87 patients per arm are needed to detect this difference. We intend to randomize 100 patients per arm to adjust for any lost to follow-up. We used PASS 15 Power Analysis and Sample Size Software (2017). NCSS, LLC. Kaysville, Utah, USA, ncss.com/software/pass.

Numeric Results for Testing Two Proportions using the Z-Test with Unpooled Variance

H0: P1 - P2 = 0. H1: P1 - P2 = D1 ≠ 0.

Target	Actual						
Diff							
Power	Power*	N1	N2	N	P1	P2	D1
Alpha							
0.90	0.90148	44	44	88	0.6870	0.3600	0.3270
0.0500							
0.90	0.90458	59	59	118	0.6870	0.4000	0.2870
0.0500							

0.90	0.90155	87	87	174	0.6870	0.4500	0.2370
0.0500							

* Power was computed using the normal approximation method.

Randomization

We intend to include 200 patients (100 per arm). Patients will be randomized in a 1:1 ratio to Standard of Care (SOC) or CT-FFR-guided management, in alternating block design to ensure equal groups periodically. The order of randomization will be generated using SAS for Windows 9.3, Cary, NC. Randomization envelopes will be generated by a Beaumont Research Biostatistician and will be opened in sequential order. Once the patient has met all the inclusion criteria, none of the exclusion criteria and has signed the informed consent, the next envelope will be opened which will contain a slip indicating the patients assigned study number and to which arm they are being randomized.

SOC Group Management

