Attending physicians will dictate SOC management according to their own clinical judgment. This could include discharge without further testing, EKG-only stress testing, stress echocardiography, stress myocardial perfusion imaging, direct admission and further noninvasive testing or CATH. In addition to standard testing, a blinded CT-FFR will be obtained for post hoc analysis, but it will not be used for patient management. Image data from our CT workstation will be sent directly to HeartFlow, Inc. over a secure research transfer node.

If attending physicians decide that SOC Group patients should undergo CATH, the protocol will specify an invasive fractional flow reserve will be performed on all lesions over 30% stenosis severity, to confirm the presence or absence of flow-limiting stenosis. This may be waived without protocol deviation if deemed unsafe by the severity of stenosis or due to clinical circumstances, as documented in a completed Physician Study Questionnaire.

CT-FFR-Guided Group Management

Patients in this group will be triaged using CT-FFR. Image data from our CT workstation will be sent directly to HeartFlow, Inc. over a secure Priority (STAT) transfer node. Interpreting physician will categorize CT-FFR results as follows:

1. CT-FFR >0.80. All CT-FFR segmental values are >0.80, with no indication of flow limiting ischemia. A non-binding recommendation that the patient undergo an initial trial of medical therapy will be made by the interpreting co-investigator. Attending physicians will be asked to complete a study Physician Questionnaire to determine whether they followed this recommendation or not, and if not, why not.
2. CT-FFR 0.70-0.80. These will be reported as values in the abnormal range without specific recommendations about whether CATH should be performed. Attending physicians will decide triage in consideration with other clinical data. Attending physicians will be asked to complete a study Physician Questionnaire to determine what clinical factors influenced their triage decision.

3. CT-FFR <0.70. These are abnormal values that are will be reported as high-risk. A non-binding recommendation that the patient undergo CATH will be made by the interpreting co-investigator. Attending physicians will be asked to complete a study Physician Questionnaire to determine whether they followed this recommendation or not, and if not, why not.

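### The diagnostic-effectiveness formulas need a CATH-FFR result for credit but divide by all CATH patients, although CATH-FFR may be waived or not required; read literally, they score some correct triage as incorrect

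*Combined protocol and SAP*

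**What the plan says.** All places are in the combined protocol and SAP.

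- **Reference standard** (Secondary Hypotheses, Diagnostic Effectiveness): "True flow-limiting coronary stenosis will be defined by CATH-FFR as the gold standard in patients undergoing CATH". The introductory text gives the threshold: "The standard cutoff for an abnormal CATH-FFR and CT-FFR is the measurement of a blood pressure drop of" at least 20%, that is, FFR at or below 0.80.
- **CT-FFR arm:** "Proportion of correct CT-FFR triage = (True positive + True negative) / All CATH". A true positive needs a positive CATH-FFR and a true negative needs a negative one.
- **SOC arm:** "Proportion of correct SOC triage = True positive / All CATH". A true positive must be confirmed by CATH-FFR, and "there can be no SOC true negative cases that go to CATH".
- **Data Analysis, Diagnostic Effectiveness** repeats the denominator: everyone sent to CATH under each strategy. It then compares, within the SOC arm, actual triage with hypothetical triage by blinded CT-FFR.
- **When CATH-FFR is absent:** SOC Group Management says "This may be waived without protocol deviation if deemed unsafe by the severity of stenosis or due to clinical circumstances", and CT-FFR-Guided Group Management has an equivalent waiver. Risks of the Study gives an overly severe lesion as an example, and does not require CATH-FFR when no lesion exceeds 30%.
- **Missing data** (Data Analysis): missing values stay missing and are not substituted.

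No section says how to classify a CATH patient whose CATH-FFR is absent or incomplete.

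**The concern.** A CATH patient without CATH-FFR enters the denominator and can never enter the numerator. Such patients are not a random subset. A waiver for severity takes credit away where flow-limiting disease is most plausible, and the no-lesion exemption takes a true negative away where disease is least plausible. The accuracy proportion then depends partly on who was measured, not only on how well patients were triaged.

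The between-arm accuracy comparison is at stake, and diagnostic effectiveness is part of the stated trial objective. The within-SOC comparison with blinded CT-FFR is affected in the same way if the same formulas are applied to all SOC CATHs. If the rule is left open, it will be chosen after the data are seen.

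**Working it through.** **1. The plan's own figures.** Sample Size blends stratum rates 2:1:
- SOC: (2 × 58.3 + 89.5)/3 = 68.7%
- CT-FFR: (2 × 21.3 + 65.6)/3 = 36.1%

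The adopted row (68.7% vs 45%, two-sided 0.05, power 90%, unpooled) gives (0.687 × 0.313 + 0.45 × 0.55) × (1.960 + 1.282)² / 0.237² = 86.5, so 87 per arm, as stated. No figure is given for diagnostic effectiveness or for CATH-FFR completeness.

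**2. Literal scoring by type of patient.**

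| At CATH | SOC | CT-FFR positive | CT-FFR negative |
|---|---|---|---|
| Truly flow-limiting, waived for severity, nothing measured | incorrect (wrong) | incorrect (wrong) | incorrect (right) |
| No lesion >30%, nothing measured | incorrect (right: SOC has no true negatives) | incorrect (right) | incorrect (wrong) |
| Flow-limiting lesion waived, another measured negative | incorrect (wrong) | incorrect (wrong) | may be credited as true negative (wrong) |
| One lesion waived, another measured positive | correct (right) | correct (right) | incorrect (right) |

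The third row shows that partly measured patients are affected too.

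**3. Cost per misscored patient.** CATHs per 100 randomized:
- SOC: 69 (Sample Size) or 58 (Risks of the Study). 1/69 = 1.4 points; 1/58 = 1.7.
- CT-FFR: 36 (Sample Size), 45 (adopted row) or 54 (Risks of the Study, 79/147, from a wider 25-99% stenosis cohort). 1/36 = 2.8 points; 1/45 = 2.2; 1/54 = 1.9.

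**4. Scale against sampling error (accuracy is assumed).** SE of the between-arm difference:
- At 60% accuracy: √(0.24/69 + 0.24/36) = 10.1 points; √(0.24/58 + 0.24/54) = 9.3. One SE equals 0.1007 × 36 = 3.6 to 0.0926 × 54 = 5.0 net misscored CT-FFR patients, or 0.0926 × 58 = 5.4 to 0.1007 × 69 = 6.9 SOC patients.
- At 80% accuracy: √(0.16/69 + 0.16/36) = 8.2 points; √(0.16/58 + 0.16/54) = 7.6. One SE equals about 3-4 CT-FFR or 4-6 SOC patients.

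**5. Within-SOC illustration.** The counts are assumed, and the hypothesis-section formulas are assumed to apply to all 69 SOC CATHs. True correct triage: SOC 41, blinded CT-FFR 50, gap 9/69 = 13.0 points. The no-lesion patients are three CT-FFR-negative patients. The severity waivers are three true positives with nothing measured, two of them CT-FFR positive.

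| Scenario | As written | Determined patients only | Severity waivers counted positive |
|---|---|---|---|
| No-lesion patients only | 47/69 − 41/69 = 8.7 | 50/69 − 41/69 = 13.0 | 13.0 |
| Severity waivers only | 48/69 − 38/69 = 14.5 | 48/66 − 38/66 = 15.2 | 50/69 − 41/69 = 13.0 |
| Both | 45/69 − 38/69 = 10.1 | 48/66 − 38/66 = 15.2 | 50/69 − 41/69 = 13.0 |

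Restricting to determined patients repairs the no-lesion error. Under severity waivers it can move the gap further from the truth.

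Bounds need care as well. With waivers only, SOC runs from 38/69 to 41/69 and CT-FFR from 48/69 to 51/69, and both ranges contain the truth. Pairing best with best gives 51/69 − 41/69 = 14.5, and worst with worst gives 48/69 − 38/69 = 14.5, so the gap appears certain when it is not. Cross-pairing gives 48/69 − 41/69 = 10.1 to 51/69 − 38/69 = 18.8.

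**The case against.** **This is an ambiguity, not an error.** No sentence calls a waived patient incorrect, and the missing-data rule could be read as leaving unmeasured patients out. That is a fair reading of one sentence. It conflicts with a denominator of all CATH patients, stated in both formulas and repeated in Data Analysis, and it would selectively remove the most severe lesions. Likewise, treating a patient with no lesion above 30% as reference negative is natural, but it is not what the formula says.

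**The effect is probably small.** The criteria exclude "CCTA lesions demonstrating stenosis >90"% and cases with an a priori recommendation or decision for CATH, so severity waivers should be uncommon. A no-lesion patient needs marked disagreement between CCTA and CATH. The outcome is secondary and has no power calculation. Waiver reasons are documented, and stenosis above 50% at CATH and PCI or CABG are reported separately. All of this stands and limits the weight of the point, but it does not supply the missing rule.

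**Stronger readings that the documents do not support.**
- *The formula penalizes the CT-FFR arm.* Severe lesions form a larger share of its expected CATHs: (65.6/3)/36.07 = 60.6%, against (89.5/3)/68.7 = 43.4% in SOC. But those CT-FFR rates are described thus: "In our previous CT-FFR negative patients, there were 65.6% CATHs in the 71-99% stenosis group and 21.3% in the 51-70% stenosis group". With equal waiver fractions among severe lesions, the sign reverses if fewer than 0.434/0.606 = 72% of waived CT-FFR-arm patients were CT-FFR positive. No direction can be claimed.
- *Within SOC, the no-lesion error runs against blinded CT-FFR alone.* That holds only if the CT-FFR formula is applied to all SOC CATHs. Data Analysis gives no formula there, and its wording could confine the blinded CT-FFR denominator to CT-FFR-positive patients, which leaves no true negatives to lose.
- *The proportion of CATH patients with a positive invasive FFR (Additional data analysis) is misscored.* It is a literal descriptive count: a waived patient has no positive result.

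**Conclusion.** The point holds. Followed as written, the formulas score some correctly triaged patients as incorrect in both arms, and can misclassify patients with a waived severe lesion and another lesion measured negative. The missing-data sentence does not resolve this.

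Only the per-patient cost can be stated: about 1.4-1.7 points in SOC and 1.9-2.8 in CT-FFR (2.2 at the 45% rate behind the adopted sample size). This rests on the plan's anticipated or historical CATH rates and 100 patients per arm. The total effect and its net sign cannot be determined. The SE comparison and the within-SOC gaps rest on assumed accuracies and counts and only show scale.

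A reader might infer that the trial's main result is in doubt. It is not: the primary CATH rate and the sample size do not use CATH-FFR.

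**What to change.** Leave the waiver as it is and change the analysis text only.

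1. **Define the reference per patient.** Positive: any measured CATH-FFR at or below 0.80, even if another lesion was waived. Negative: every lesion above 30% measured and above 0.80, or no lesion above 30%. Otherwise: undetermined. As a stated endpoint definition, this does not conflict with the no-substitution rule.
2. **Change the denominator** in both formulas and in Data Analysis to CATH patients with a determined reference. Report undetermined patients by arm and documented waiver reason.
3. **Always show beside it** (a) best-case and worst-case proportions over all CATH patients, with bounds on a difference pairing one side's best case with the other's worst; and (b) one analysis counting severity waivers as reference positive, correct for CT-FFR only if CT-FFR was positive. The determined-only estimate should not stand alone, because it omits severity-waived patients.
4. **Apply the same rules to the SOC actual-versus-blinded CT-FFR comparison** and state its denominator.
5. **Keep the proportion with a positive invasive FFR as a descriptive count,** reported with the number who had no CATH-FFR.

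Cost: a few extra analyses and wider stated uncertainty. The Physician Study Questionnaire already has to record the waiver reason; the form is not in the documents, so whether it codes severity separately must be checked.

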Risks Associated with Heart Catheterization and Invasive Fractional Flow Reserve

Common (more than 10%)

- warm feeling or flushed feeling during adenosine infusion (which is part of the FFR study)
- lightheadedness
- nausea
- pain
- discomfort
- bruising or bleeding where the catheter is inserted in the groin
- radiation equivalent to 3-5 years of natural background radiation

Rare (less than 1%)

- contrast (dye) allergy
- diaphoresis (temporary excessive sweating)
- atrioventricular block -impaired conduction of the impulse that regulates the heartbeat (from adenosine)
- contrast induced nephropathy (deterioration of kidney function due to contrast exposure)
- hives (for those allergic to contrast dye)
- thrombosis (blood clots resulting in reduced blood flow)
- artery dissection (damage to the artery wall)
- perforation (a hole in the artery)
- stroke
- myocardial infarction (heart attack)
- death

Internal Safety Monitoring Committee

An Internal Safety Monitoring Committee will conduct regularly scheduled reviews of the safety of patients. Two physicians and a statistician who are not co-investigators will be included. Members will monitor safety outcomes, enrollment and completeness of follow-up. The Committee will meet after the first 20 patients and after each 40 subsequent patients till the study is completed. Any MACE event or major adverse outcome will be reported immediately to the Committee. The results of all Committee meetings will be provided to the IRB.

Data Analysis

Descriptive statistics will be given for all variables collected including indications for the test, demographics, patient history, CTA tech information, details from the physicians reading form, and from the CT-FFR. Missing data will remain missing and will not be replaced by substitutions or interpolation. Categorical variables will be summarized as counts and percentages. All continuous variables will be

summarized as means+/- the standard deviation where normal or median and 25th, 75th percentiles if not normal. The minimum and maximum will also be provided.

Catheterization Rate: The primary outcome will be examined between the 2 randomization arms using Pearson's Chi-square test. The Odds ratio and 95% confidence interval will also be reported.

Diagnostic Effectiveness: The secondary outcome will be defined as the proportion of accurate triage using CATH-FFR as the gold standard among all patients triaged to CATH by each strategy.

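### Optional gain: the valid unstratified primary test leaves out CCTA stenosis group; an uncorrected Cochran-Mantel-Haenszel test would change power by about -1 to +3 points at the 45% planning row and would usually sharpen the risk difference

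*Combined protocol and SAP*

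**What the plan says.** For the catheterisation rate, the Data Analysis section states: "The primary outcome will be examined between the 2 randomization arms using Pearson's Chi-square test". It adds: "The Odds ratio and 95% confidence interval will also be reported". No stratified or adjusted primary analysis is described, and the Randomization section mentions blocks but no stratification by stenosis.

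Stenosis group appears in two other places. The Primary Hypothesis says: "There will be a pre-specified subset analysis of the Intermediate (51-70%) and Severe (71-90%) stenosis groups". The Sample Size section builds both planning rates from it: "the SOC arm had a 89.5% CATH rate in the 71-99% stenosis group and 58.3% in the 51-70% stenosis group", then "In our previous CT-FFR negative patients, there were 65.6% CATHs in the 71-99% stenosis group and 21.3% in the 51-70% stenosis group", weighted by "With the 51-70% stenosis group having twice as many patients as the 71-99% group".

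The group limits do not match across sections. The study population is "found to have 50% or greater stenosis but less than 90% of at least one coronary branch", the exclusion is worded as "CCTA lesions demonstrating stenosis >90" per cent, and the subsets start at 51%.

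**The concern.** Stenosis group is the only baseline factor for which the protocol gives CATH rates, and the gaps are wide: 31.2 points in the standard-of-care (SOC) arm (89.5 - 58.3) and 44.3 points in the CT-FFR figures (65.6 - 21.3). The reading exists for every patient, because inclusion criterion 3 requires it. The plan uses the factor to set the sample size and to define subsets, but not in the primary test. Spread in outcome that stenosis explains, and any chance imbalance in severity between arms, therefore stays in the error of the comparison.

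At stake is a little power and some precision on the risk-difference scale. Validity is not at stake.

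**Working it through.** **Inputs from Sample Size.** SOC 0.583 and 0.895; CT-FFR 0.213 and 0.656; severe share 1/3; planning row 0.687 against 0.45; 87 evaluable and 100 randomised per arm; two-sided 0.05. The documents give no split of the 45% by stenosis group, so the splits below are assumptions.

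**1. The plan's own figures.** SOC: (2 × 58.3 + 89.5)/3 = 68.7%. CT-FFR: (2 × 21.3 + 65.6)/3 = 36.1%. Unpooled power = Φ(d/√(Σp(1-p)/n) - 1.96). Here Σp(1-p) = 0.687 × 0.313 + 0.45 × 0.55 = 0.4625, so 0.237/√(0.4625/87) = 3.250 and Φ(1.290) = 0.9015. The plan prints 0.90155, so it reproduces.

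**2. What stratifying removes.** The risk-difference variance falls by roughly w(1-w)(g₁² + g₂²)/n, where w = 1/3 and g₁, g₂ are the gaps between stenosis groups in each arm. The half-width of the 95% interval at 100 per arm is 1.96√(V/100), where V is the variance multiplied by n.

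- 45% row, crude: V = 0.4625, half-width 13.3 points.
- 45% row, constant risk ratio (38.2%/58.6%): V = 0.4625 - (2/9)(0.312² + 0.204²) = 0.4316, half-width 12.9.
- 45% row, planning rates shifted on the logit scale (30.0%/75.1%): V = 0.4625 - (2/9)(0.312² + 0.451²) = 0.3957, half-width 12.3.
- 36.1%: V goes from 0.4456 to 0.4456 - (2/9)(0.312² + 0.443²) = 0.3804, half-width 13.1 to 12.1.
- Assumed small gap (SOC 63%/80%, CT-FFR 38%/59%, which also average 68.7% and 45%): the ratio of variances is about 0.965.

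Simulation, which allows for finite group sizes, gives slightly smaller reductions (last column below), and 12.4 to 12.9 points for the 45% row.

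**3. Power by simulation.** At least 200,000 trials per case, allocation not stratified, both tests without continuity correction. Each cell shows Pearson, then CMH.

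| Case | 87 per arm | 100 per arm | Variance ratio |
|---|---|---|---|
| 45%, constant risk ratio 38.2/58.6 | 89.8 → 90.7% | 93.2 → 94.1% | 0.94 |
| 45%, constant risk difference 34.6/65.8 | 89.8 → 91.6% | 93.2 → 94.8% | 0.91 |
| 45%, constant odds ratio 30.9/73.2 | 89.9 → 92.7% | 93.3 → 95.6% | 0.88 |
| 45%, logit shift 30.0/75.1 | 89.8 → 92.9% | 93.3 → 95.8% | 0.87 |
| 36.1%, planning rates 21.3/65.6 | gain under 0.4 points | gain about 0.2 points | 0.86 |
| 45%, small gap | 89.8 → 89.9% | 93.2 → 93.4% | 0.97 |
| 45%, no gap | 89.9 → 89.1% | 93.2 → 92.8% | 1.005 |

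Type I error is about 5% for both tests. Repeat runs move the gains by about a tenth of a point.

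**4. Sensitivity.**

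- *Severe share.* With the SOC gap kept but the severe share assumed to be 20%, the gain is about 0.7 to 1.4 points. At 10% it is about zero. Overall rates move with the share in these cases.
- *Extreme splits of the 45%.* With the SOC gap kept, a CT-FFR rate of 45% in both groups gives -0.4 to 0.0 points. Placing the whole effect in the intermediate group gives +5.3 (87 per arm) or +4.0 (100 per arm).
- *Continuity correction.* At 87 per arm a corrected CMH test has 87.9% to 90.3% power against Pearson's 89.9%, so most or all of the gain disappears.
- *Odds ratio at 100 per arm, 45% row.* Crude: (0.45/0.55)/(0.687/0.313) = 0.37. Stratified: 0.31 to 0.35. The log-scale standard error rises from 0.296 to between 0.310 and 0.325. At 36.1% it rises from 0.301 to 0.340.

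**The case against.** The strongest reply is that this is a choice between two valid tests. Enrolling 100 per arm already gives Pearson about 93% power at the 45% row and over 99% at the expected 36.1%. The only effect measure planned is an odds ratio, whose log-scale interval gets slightly wider. Stenosis is already examined in the subsets. All of that is true, and it is why the point is optional.

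The reply is also right that the planning gap may not carry over. The source band is 71-99%, whereas lesions above 90% are excluded. The CT-FFR rates are labelled as coming from CT-FFR negative patients. Exclusions 2 and 3 remove patients with an a priori CATH recommendation or decision, and the documents do not say whether the earlier cohort did the same. These exclusions could shrink both the gap and the severe share, so a gain of 3 points should not be promised.

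What survives is that the change is nearly free, its worst modelled loss is under 1 point of power, and the risk difference becomes more precise in every case examined in which stenosis predicts CATH in both arms.

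A reader might go further and infer that the primary test is invalid or underpowered, or that unstratified randomisation biases it. The documents do not support that: type I error is about 5%, the stated power reproduces, and randomisation already covers chance imbalance in severity.

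**Conclusion.** The primary analysis is sound, and stratifying it is an inexpensive improvement. At the 45% row, with the documents' SOC gap and 2:1 mix, the gain is about 1 to 3 points over plausible splits of the 45%. It is 0 to 0.3 points with the assumed small gap, and a loss of 0.4 to 0.9 points if stenosis does not predict CATH. Power is already near its ceiling at 36.1%.

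The better reason to change is precision. Risk-difference variance falls 6% to 14% at the documents' gap and mix, and about 3% with a small gap. All figures at 45% rest on assumed group rates, and all power gains rest on omitting the continuity correction. It would be wrong to conclude that the planned odds-ratio interval becomes narrower.

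**What to change.** Before any outcome comparison by arm, amend the SAP as follows.

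- Make the primary test a Cochran-Mantel-Haenszel test, stated explicitly to be without continuity correction, stratified by the most severe lesion on the qualifying CCTA: 50% to 70%, and above 70% (including any enrolled patient with a lesion at exactly 90%).
- Use the same two groups for the pre-specified subset analysis, so that no enrolled patient, such as one at exactly 50%, falls outside them.
- Report the Mantel-Haenszel risk difference with its 95% interval, and show the stratified odds ratio beside the crude one.
- Keep Pearson's test as a sensitivity analysis.

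The cost is SAP wording, since the CCTA reading is already required for entry. The downsides are a main odds ratio that becomes stratum-adjusted with a slightly wider log-scale interval, one more effect measure to report, and under 1 point of power lost if stenosis group turns out not to predict CATH.
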